#### **4.1.5 Baseline Characteristics**

##### **4.1.5.1 Definitions and Derivations**

Participant characteristics at baseline height [cm], weight [kg] and weight category and COVID-19 vaccination status at baseline will be listed and summarized.

Quantitative summary of height and weight will be computed by cohort and weight category.

##### **4.1.5.2 Presentation**

Both listings and summaries will be presented for the SAF.

A summary of demographics for those participants with a positively adjudicated Cardiovascular (CV) event will be presented.

#### **4.1.6 Disease Characteristics**

##### **4.1.6.1 Definitions and Derivations**

COVID-19 status (Negative/Positive) will be determined at screening for all participants and severity for those assigned to Cohorts 2 and 3. A COVID-19 symptom screen is performed for occurrence and severity of COVID-19 symptoms (none, mild, moderate, severe, unknown). The symptom screen is also performed when Cohort 1 participants develop at least one of the below symptoms post Day 1.

- Symptoms of any duration
  - Fever
  - Shortness of breath
  - Difficulty breathing
- Symptoms present for 2 or more days
  - Chills
  - Cough
  - Fatigue
  - Muscle aches
  - Body aches
  - Headache
  - New loss of taste
  - New loss of smell
  - Sore throat

##### **4.1.6.2 Presentation**

Each symptom will be summarized qualitatively by category (none, mild, moderate, severe, unknown). For Cohorts 2 and 3, the summary will include only the screening visit. For subjects of Cohort 1, the summary will be calculated for occurrence at any time after Day 1.

#### **4.1.7 Medical History and Concomitant Disease**

##### **4.1.7.1 Definitions and Derivations**

Disease related medical history (past, ie, started and stopped before treatment and current, ie, started before study and ongoing at treatment visit) will be coded using MedDRA version 24.1 or higher.

#### **4.1.7.2 Presentation**

All related medical history will be listed including visit, description of the disease/procedure, MedDRA SOC, PT, start date and stop date (or ongoing, if applicable). Number of subjects with a history or concomitant condition will be counted by SOC and PT and by cohort.

A summary of medical history for those participants with a positively adjudicated Cardiovascular (CV) event will be presented.

#### **4.1.8 Prior and Concomitant Medications**

##### **4.1.8.1 Definitions and Derivations**

Any medication or vaccine (including over-the-counter or prescription medicines, vitamins, and/or herbal supplements) that the participant is receiving at the time of enrollment or receives during the study will be recorded along with:

- Reason for use
- Dates of administration including start and end dates
- Dosage information including dose and frequency

Prior medications are those with start and stop date before the day of treatment.

Concomitant medications are any medications taken at least once between day of treatment (inclusively) and end of the follow-up period. Ie, medications with start date prior to Day 1 and ongoing, medications with start date between Day 1 and day of Visit 6 (or early discontinuation).

The duration of the medication will be calculated as:

$$\text{Duration} = (\text{end date/time}) - (\text{start date/time}) + 1$$

The duration may be presented in hours or days in the listing depending on the applicability to the emerging data. For medications with partial or completely missing start date/times and/or end date/times, the duration will not be calculated.

Prior and concomitant medications will be coded using the AstraZeneca dictionary.

##### **4.1.8.2 Presentation**

Prior and concomitant medications will be listed by participant and will include the following information: reported name, preferred term, the route of administration, dose, frequency, start date/time, duration, and indication.

The number of participants exposed to a medication will be presented for each occurring coded term of prior/concomitant medications. The percentage will be based on the number of subjects in each cohort in the SAF.

#### 4.1.9 Study Drug Compliance

##### 4.1.9.1 Definitions and Derivations

No analysis for study drug compliance is planned as the drug is only administered once.

##### 4.1.9.2 Presentation

Not applicable.

### 4.2 Endpoint Analyses

This section covers details related to the endpoint analyses such as primary, secondary, other endpoints. Sensitivity analyses are done by repeating the endpoint analyses using a sensitivity analysis set if indicated in [Table 2](#). The analysis sets shown are applicable to the tables of the endpoints. Listings may utilize other sets. All endpoint analyses will be descriptive qualitative or quantitative summaries.

**Table 2: Analysis Endpoints**

Objectives	Endpoints	Analysis Set
Primary		
To evaluate the serum concentrations of AZD7442 after a single IM or IV dose in pediatric participants	Serum concentrations of AZD7442 at specified time points during the one-year study period when administered as a single IM or IV dose  Serum PK parameters (if data permits): Cmax, tmax, t1/2, AUC0-last , AUC0-inf , tlast, %AUCext, and: 

• for IM: CL/F, and Vz/F

• for IV: CL, and Vss

 Model-derived predicted serum AZD7442 concentrations, Cmax and AUC0-inf	PKS
To evaluate the safety and tolerability of AZD7442 after a single IM or IV dose in pediatric participants	TEAEs, SAEs, and AESIs (including anaphylaxis, injection/infusion site reactions, MIS-C).  Safety laboratory parameters (hematology, clinical chemistry, coagulation, and urinalysis); 12 lead safety ECG; vital signs (BP, pulse rate, tympanic membrane temperature, and respiratory rate), and physical examination.	SAF
Secondary – All Cohorts		

Objectives	Endpoints	Analysis Set
To evaluate the PD of AZD7442 after a single IM or IV dose	Titer of SARS-CoV-2 neutralizing antibodies	SES
To evaluate the immunogenicity profile of AZD7442	Incidence of ADA and nAb to AZD7442 in serum	ADS1/2/3
Secondary – Cohort 1 (Prophylaxis)		
To evaluate the incidence of SARS-CoV-2 infections with or without COVID-19 symptoms after a single IM or IV dose of AZD7442 in pediatric participants	Incidence of SARS-CoV-2 infections with and without COVID-19 symptoms	SAF, mFAS
Secondary – Cohort 2 and Cohort 3 (Treatment)		
To quantify SARS-CoV-2 viral loads after a single IM or IV dose of AZD7442 in pediatric participants	Change from baseline to Day 8 in viral load as measured by qRT-PCR.	SAF
To evaluate the proportion of participants with progression of COVID-19 after a single IM or IV dose of AZD7442 in pediatric participants	Proportion of participants with progression of COVID-19 through Day 29	SAF
To evaluate COVID-19 related death through 90 days after a single IM or IV dose of AZD7442 in pediatric participants	The incidence of COVID-19-related death occurring after dosing with IMP up to study day 90	SAF
Secondary – Cohort 3 (Severe COVID-19)		
To evaluate the time to sustained recovery from severe COVID-19 after a single IM or IV dose of AZD7442 in pediatric participants	Time to sustained recovery (defined as being discharged from the index hospitalization, followed by being alive and home for 14 consecutive days)	SAF
Exploratory		
To evaluate the concentrations of AZD7442 in nasal fluid after a single IM or IV	Nasal concentrations of AZD7442 at specified time points during the one-year study period when administered as a single IM or IV dose	SAF

Objectives	Endpoints	Analysis Set
dose in pediatric participants		

#### 4.2.1 Primary PK Endpoints

To evaluate the serum concentrations of AZD7442 after a single IM or IV dose in pediatric participants, the primary PK endpoints serum AZD7442 concentrations and PK parameters derived from these by non-compartmental analysis in accordance with AstraZeneca Pharmacokinetic Evaluations in Clinical Trials guideline will be listed and presented separately in tabular and graphical form.

Any serum concentrations for AZD7442 will be reported as the individual component concentrations AZD8895 and AZD1061 as well as the sum of the two individual component concentrations labelled as AZD7442.

The analysis of these endpoints will comprise of descriptive summary statistics stratified by cohort, route of administration (IM or IV) and weight categories (1, 2, 3, 4 and all).

For PK parameters other than *tmax* and *tlast*, the following descriptive statistics will be presented: *n*, gmean, gSD, 95% CI for the gmean, gCV, arithmetic mean, arithmetic SD, median, minimum, and maximum. For *tmax* and *tlast*, only *n*, median, minimum, and maximum will be presented.

##### 4.2.1.1 Serum Concentration Data

For AZD7442 mAbs, the serum concentrations for each scheduled time point will be summarized based on the PKS.

A listing of all serum concentration-time data, ie, PK scheduled times, actual sample collection times, sample actual relative times (ie, relative to time of administration of the IMP), as well as derived sampling time deviations (ie, difference between actual and scheduled time) will be presented for all participants in the SAF.

##### 4.2.1.2 Figures for Serum Concentration Data

Individual serum concentration-time data (AZD7442, AZD8895 and AZD1061) will be graphically presented on linear and semi-logarithmic scales, for all participants in the PKS. Combined individual serum concentration versus actual times will be plotted on both the linear and semi-logarithmic scales for all participants in the PKS. Plots will be grouped by cohort, route of administration and weight categories. Figures for the gmean ( $\pm$ gSD) serum concentration-time data will be presented by cohort, route of administration and weight categories (1, 2, 3, 4 and all) on both a linear and semi-logarithmic scale (no gSD presented for the semi-logarithmic scale), for all participants in the PKS.

#### 4.2.1.3 Serum Pharmacokinetic Parameters

All reportable AZD7442, AZD8895 and AZD1061 PK parameters, obtained by non-compartmental analysis method, including individual diagnostic and  $\lambda z$ -related parameters, will be listed for each participant by cohort, route of administration and weight categories, based on the PKS. All PK parameters will be summarized based on the PKS.

**Table 3: PK Parameters**

Parameter	Definition	Calculation
Cmax	Maximum observed serum (peak) drug concentration	
Clast	Last observed (quantifiable) concentration	
Ctrough	Observed drug concentration at the end of a specified time interval that is indication specific	For cohort 2 and 3 (treatment): concentration 28 days post-dose For cohort 1 (prophylaxis): concentration 182 days post-dose
tmax	Time [days] to reach peak or maximum observed concentration following drug administration	
AUC(0-92d)	area under the serum concentration-time curve from time zero to day 92	Using the linear up/log down trapezoidal rule
AUC0-last	Area under the serum concentration-time curve from time zero to time of last quantifiable concentration	Using the linear up/log down trapezoidal rule
AUC0-inf	Area under serum concentration-time curve from time zero to infinity	Calculated by AUC(0-t) and then extrapolated by Clast/ $\lambda z$ to infinity
tlast	Time of last quantifiable serum concentration [days]	
%AUCext	percentage of AUC extrapolated	
$\lambda z$	Terminal elimination rate constant	Estimated from linear regression of the terminal part of the log concentration versus time curve
$t_{1/2} \lambda z$	Half-life associated with terminal slope ( $\lambda z$ ) of a semi-logarithmic concentration-time curve (final analysis only) [days]	$\ln 2 / \lambda z$
MRT	Mean residence time	
CL/F (for IM)	Apparent total body clearance of drug from serum after extravascular administration	Dose/AUC0-inf

Parameter	Definition	Calculation
Vz/F (for IM)	Volume of distribution (apparent) following extravascular administration (based on terminal phase)	Dose/( $\lambda z * AUC_{0-inf}$ )
CL (for IV)	Total body clearance of drug from serum after intravenous administration	DoseIV / AUC 0-inf
Vss (for IV)	Volume of distribution at steady state after intravenous administration	MRT * CL

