4.2.1 Rationale for Choice of Endpoints

The endpoints chosen for this Phase I PK/PD and safety study are consistent with those in AZD7442 studies in adults.

The primary study PK endpoints are those required to characterize the PK profile of AZD7442 following a single IM or IV dose administered to pediatrics aged \geq 29 weeks GA to < 18 years (Day 1 through Day 366). Pharmacokinetic sampling will be kept to a minimum due to the age of the population under study: one sample on Day 1 for participants receiving an IV infusion, one sample during the first 2 weeks for all participants (at either Day 4, 8, 11, or 15, spread across participants), then one sample at Day 31, 92, 183, and 366 (ie, the total number of samples per participant is up to 5 samples for IM administration and 6 samples for IV administration due to the additional sample taken at the end of the infusion on Day 1). Pharmacokinetic data will be analyzed by population methods and if data permit by non-compartmental analysis approach. This sampling scheme also enables serum AZD7442 concentration data to be obtained at the time points of primary efficacy endpoint evaluation for prophylaxis and treatment in the adult program. Pharmacokinetic profiles of AZD7442 are expected to be similar across the prophylaxis and treatment populations recruited because AZD7442 is cleared via nonspecific intracellular metabolism and will not be affected by binding to the exogenous target SARS-CoV-2. Therefore, PK data will be pooled across the cohorts within each age group.

The PD markers that are measured in this PK/PD and safety study will be used to support the assumption that the exposure-response relationship is similar for adults and children. In SARS-CoV-2 infected and non-infected children, the SARS-CoV-2 neutralizing antibody titer will be measured in a validated live neutralization assay. In addition, the neutralizing antibody titer will be correlated to the serum AZD7442 concentration. The correlation between drug level and neutralizing antibody titer in children will be compared to the correlation derived in adult serum samples.

The measures of viral load, disease progression or recovery, SARS-CoV-2 infections, and COVID-19-related death mirror the endpoints in the adult studies with AZD7442.

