8.5.1 Total Blood Volume

Blood volume estimates are provided in **Table 16**. For participants other than neonates, the total estimated blood volume to be collected during the study is approximately 73 mL per participant. For neonates, only safety and PK samples will be collected and the total estimated blood volume to be collected during the study is approximately 22 mL per participant. The total volume can be adjusted by age and the body weight of the participant per local ethics requirements. Where necessary, the visit windows in the SoA can be used to collect samples across a number of days. When sample collection occurs over ≥ 2 days for a given study visit, participants are required to visit the site at least once per study visit. If practical, additional sample collection can take place at home visits as long as the samples are obtained per protocol by qualified personnel. If it is not possible to obtain sufficient blood from a participant at a given study visit, the order of the samples will be prioritized according to the key requirements of the study and the following hierarchy will be applied: safety (ie, serum chemistry, hematology, coagulation), PK, SARS-CoV-2 neutralizing antibodies, and ADA (see Laboratory Manual). For participants receiving IV infusions of AZD7442, blood samples are to be collected from the opposite side of the body to the IV infusion at Visit 1.

Table 16 Blood Volume Estimates

Visit (study day \pm visit window)	Estimated blood volume for neonates ^a	Estimate blood volume for all other participants ^b
Screening Visit (Day -7 to Day 0)	3.7 mL	6.3 mL
Visit 1 (Day 1 \pm 0)	1.2 mL (IV only)	6.0 to 8.5 mL ^{c, d}
Visit 2 (Day 4 to 15 \pm 2)	1.2 mL	2.5 mL
Visit 3 (Day 31 + 5)	4.9 mL ^e	14.8 mL
Visit 4 (Day 92 \pm 5)	2.6 mL ^e	10.3 to 12.8 mL ^d
Visit 5 (Day 183 \pm 10)	3.5 mL ^e	13.0 mL
Visit 6 (Day 366 \pm 15)	4.9 mL ^e	14.8 mL
Total from screening to Day 366	20.8 to 22.0 mL	67.7 to 72.7 mL

^a For neonates, only safety and PK samples will be collected.

^b For participants other than neonates, the following hierarchy will apply if it is not possible to obtain blood for all samples: (1) safety, (2) pharmacokinetics, (3) SARS-CoV-2 neutralizing antibodies, and (4) anti-drug antibodies.

^c At Visit 1, participants receiving AZD7442 IV will have an extra 2.5mL blood sample taken for post-dose PK sampling.

^d At Visit 4, participants in Cohort 1 will also have an additional 2.5mL taken for SARS-CoV-2 serology.

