8.5.2 Pharmacokinetics

- Serum samples will be collected for measurement of serum concentrations of AZD7442 (AZD8895 and AZD1061) at either Day 4, 8, 11, or 15 (one sample) and Days 31, 92, 183, and 366 (one sample on each day), as specified in the SoA (Section 1.3). For participants who receive AZD7442 via an IV infusion, a serum sample should also be taken at the end of the infusion on Day 1 from the opposite side of the body. Serum samples should still be taken even if the participant is outside the visit window specified in the SoA.
- Samples may be collected at additional time points during the study if warranted and agreed upon between the Investigator and the Sponsor, eg, for safety reasons. The timing of sampling may be altered during the course of the study based on newly available data (eg, to obtain data closer to the time of peak or trough matrix concentrations) to ensure appropriate monitoring.
- Serum samples will be used to assess the PK of AZD7442 following IM and IV administration. Samples collected for analyses of AZD7442 serum concentration may also be used to evaluate safety or efficacy aspects related to concerns arising during or after the study.
- Samples will be collected, labeled, stored, and shipped, as detailed in the Laboratory Manual.
- AZD7442 PK parameters (eg, maximum serum concentration, AUC), if data permit, will be calculated based on AZD7442 serum concentrations following IM and IV administration.

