### **3.3.4 Study Day**

Study Day 1 is defined as the date of first dose of IMP.

For visits (or events) that occur on or after first dose of study treatment, study day is defined as (date of visit [event] – date of first dose of study treatment + 1). For visits (or events) that occur prior to first dose, study day is defined as (date of visit [event] – date of first dose of IMP). There is no study day 0 defined for this study.

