D8850C00006 Open-label, Uncontrolled, Single dose Study to Evaluate the Pharmacokinetics, Pharmacodynamics, and Safety of AZD7442 in Pediatric Participants Aged $\geq$ 29 Weeks Gestational Age to < 18 Years	IM and IV; dose is dependent on cohort indication and participant's weight. PK samples collected at end of infusion (IV only), on either 3, 7, 10 or 14 days post-dose, and then 28, 91, 182, and 365 days post-dose	~100 a	Phase I, pre-exposure prophylaxis, Treatment of COVID-19 in non-hospitalized participants, Treatment of COVID-19 in hospitalized participants

a The enrolment for this study was stopped early due to FDA feedback, therefore the full analysis set will only contain 46 participants.

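### SAP Tables 3 and 5 place the treatment-cohort Ctrough sample at 28 days post-dose, but the protocol schedules it at Day 31 (+5), which is 30 to 35 days post-dose

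*SAP*

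**What the plan says.** SAP section 4.2.1.3, Table 3, defines Ctrough as "Observed drug concentration at the end of a specified time interval that is indication specific". For the treatment cohorts the entry reads "For cohort 2 and 3 (treatment): concentration 28 days post-dose". For prophylaxis it is the concentration at 182 days.

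SAP Table 5 (appendix) describes this study's own PK samples, after the end-of-infusion sample for IV participants, as taken "on either 3, 7, 10 or 14 days post-dose, and then 28, 91, 182, and 365 days post-dose".

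The protocol gives a different time for the third of these. Section 4.2.1 has one sample in the first two weeks and "then one sample at Day 31, 92, 183, and 366". Section 8.5.2 repeats "Days 31, 92, 183, and 366 (one sample on each day), as specified in the SoA". Protocol Tables 2, 3 and 16 give Visit 3 a window of +5 days with no negative side.

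SAP section 3.3.4 fixes the day count: "Study Day 1 is defined as the date of first dose of IMP". SAP section 3.3.6 analyses scheduled visits as they are recorded in the eCRF. The SAP gives no window, nearest-visit rule or interpolation rule for Ctrough.

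**The concern.** A parameter defined as an observed concentration at a fixed time needs a sample at or near that time, or a rule that says which sample stands in for it. For the treatment cohorts the SAP has neither. Whoever programs Table 3 must choose between two readings that the plan does not settle:

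- **Literal.** Ctrough is missing for each Cohort 2 participant who attended Visit 3 on schedule.
- **Loose.** The Visit 3 value is used, and a concentration from 30 to 35 days is labelled as a 28-day one.

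Section 4.2.1.3 says that all PK parameters will be summarised, so the choice will appear in an output. The label matters because both adult treatment studies in SAP Table 5 have a PK sample at 28 days. A reader who sees a pediatric 28-day figure may set it beside those samples without knowing that the times differ.

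**Working it through.** **Inputs.** Protocol PK days: 4, 8, 11 or 15, then 31, 92, 183, 366 (sections 4.2.1 and 8.5.2). Windows: ±2 days at Visit 2 and +5 days at Visit 3 (Tables 2 and 3). Day 1 is the dosing day (SAP 3.3.4). SAP times: Tables 3 and 5. Half-life: protocol 4.2.1 equates the study duration with approximately 4 half-lives.

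**Step 1: reproduce the SAP Table 5 times.** Days post-dose = study day − 1.

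| Protocol day | Days post-dose | SAP Table 5 | Match |
|---|---|---|---|
| 4 | 3 | 3 | yes |
| 8 | 7 | 7 | yes |
| 11 | 10 | 10 | yes |
| 15 | 14 | 14 | yes |
| 31 | 30 | 28 | **no** |
| 92 | 91 | 91 | yes |
| 183 | 182 | 182 | yes |
| 366 | 365 | 365 | yes |

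Seven of eight times convert exactly, so the SAP uses this convention and the 28 is not a different way of counting. The prophylaxis Ctrough (182 days = Day 183) is consistent. The value 28 corresponds to Day 29 (29 − 1 = 28). The protocol's amendment history explains this: Visit 3 was moved from Day 29 to Day 31 in Version 3.0 (03 March 2022). SAP section 1 lists that amendment among the documents it is based on.

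**Step 2: does any scheduled window contain 28 days?**

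- Latest Visit 2 sample: Day 15 + 2 = Day 17, which is 16 days post-dose.
- Visit 3: Day 31 to Day 36, which is 30 to 35 days post-dose.
- The gap from 16 to 30 days contains 28. Visit 3 is 30 − 28 = 2 to 35 − 28 = 7 days late against the SAP's time.

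**Step 3: size if Visit 3 is labelled as 28 days.** Assume log-linear terminal decline, so that the ratio to the 28-day concentration is 2^(−(t − 28)/h). The protocol implies h = 365/4 = 91.25 days. The documents give no range for h, so 60 and 120 days are assumptions.

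| Half-life (days) | t = 30 | t = 35 | Visit 3 lower by |
|---|---|---|---|
| 60 (assumed) | 0.977 | 0.922 | 2.3% to 7.8% |
| 91.25 (implied) | 0.985 | 0.948 | 1.5% to 5.2% |
| 120 (assumed) | 0.988 | 0.960 | 1.2% to 4.0% |

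Across the assumed range the difference is 1.2% to 7.8%. The formula does not hold near an absorption peak. The planned model has two compartments and an absorption parameter (SAP 4.2.1.7.4 and 4.2.1.5), and the documents give no tmax for IM dosing.

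**The case against.** The strongest reply is that little depends on this. Ctrough is not among the PK parameters named as endpoints in protocol Table 4 or SAP Table 2; it is one row of SAP Table 3. Model-derived concentrations are already a primary endpoint, actual sampling times are listed, individual profiles are plotted against actual time, and the Visit 3 concentration is summarised as a scheduled time point in any case. A population PK analysis that uses actual times is unaffected. The percentages are also small beside the study's own precision target, a 95% CI for geometric mean clearance within 60% to 140% of the estimate. All of this stands, and it limits the consequence. It does not make the parameter derivable as written.

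Three stronger readings are tempting, but the documents do not support them:

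- **On-time samples could be dropped from the PK set.** A reader might infer this from the planned listing of sampling-time deviations and from SAP 4.1.3.1. But important deviations are deviations from the protocol, whose visit is Day 31 (+5), and only time-window deviations expected to influence key assessments count. Table 5 is a brief description of studies for the population PK dataset; nothing makes it the source of scheduled times.
- **Pediatric troughs will be biased low against adults.** No adult-versus-pediatric Ctrough comparison is planned, and the direction depends on terminal decline, which is not established for IM dosing.
- **Protocol 4.2.1 is wrong that the scheme** "enables serum AZD7442 concentration data to be obtained at the time points of primary efficacy endpoint evaluation for prophylaxis and treatment in the adult program". The documents do not state the day of the adult treatment primary endpoint. SAP Table 5 gives adult PK sampling days, which are a different thing.

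**Conclusion.** The conflict is real and lies between current SAP text and current protocol text. The treatment-cohort Ctrough is defined at a time for which no scheduled sample exists, and no rule resolves it. It is wrong as written, not merely short of detail.

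Its reach is limited. Cohort 3 has no participants (SAP section 2), so only Cohort 2 is affected; the full analysis set is 46 participants across all cohorts, and the documents do not give Cohort 2's share. An unscheduled, out-of-window or early-discontinuation sample, or one taken under the earlier visit day, could fall at 28 days by chance; the documents do not say whether any did.

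The Visit 3 value would be about 1.5% to 5.2% below the 28-day value at a half-life of about 91 days, or 1.2% to 7.8% below for an assumed 60 to 120 days. Both ranges assume terminal decline by day 28 and a sample inside the Visit 3 window. For IM doses neither size nor sign can be stated.

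**What to change.** 1. In SAP Table 3, define the observed treatment Ctrough as the Visit 3 concentration, nominally 30 days post-dose with a window of 30 to 35 days, and carry that label into the table shells.
2. If a 28-day figure is wanted to line up with the 28-day adult treatment samples, report the population-PK individual predicted concentration at 28 days as a separate quantity, named as a prediction. This leaves Ctrough an observed parameter.
3. In SAP Table 5, change this study's entry from 28 to 30 (+5) days post-dose.

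The cost is two SAP table entries and matching output labels, plus one optional derived value from a model that is already planned. It needs no new samples and no protocol change.

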6.3 Measures to Minimize Bias: Randomization

This is an open-label study and all eligible participants will receive AZD7442.

For the PK sample collected post Day 1 during the first 14 days, participants will be randomized to have a blood sample collected on either Day 4, Day 8, Day 11, or Day 15 (1:1:1:1) using the IRT.

The Investigator(s) will:

- 1 Obtain signed informed consent or assent from the potential participant, or their guardian/legal representative, before any study specific procedures are performed.
- 2 Determine participant eligibility.
- 3 Assign the eligible participant unique SID via the IRT.
- 4 Participants will be allocated to receive AZD7442 administered IM or IV
- 5 Participants will be assigned the Day of PK sampling (Day 4, Day 8, Day 11, or Day 15)

If a participant withdraws from the study, then his/her enrollment/SID cannot be reused. Withdrawn participants will not be replaced.

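### For IM participants the pooled NCA tmax reflects the sampling days, not the time of peak; it should be shown by assigned day or taken from the population model

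*SAP*

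**What the plan says.** **Sampling.** Protocol 4.2.1 gives "one sample on Day 1 for participants receiving an IV infusion" and none that day for IM. Protocol 6.3 states that "participants will be randomized to have a blood sample collected on either Day 4, Day 8, Day 11, or Day 15 (1:1:1:1) using the IRT". After that, Protocol 4.2.1 has "then one sample at Day 31, 92, 183, and 366". Day 1 is the dosing day, so the early sample falls 3, 7, 10 or 14 days post-dose and the next one 30 days post-dose. The visit windows are ±2 days for Visit 2 and +5 days for Visit 3.

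**Endpoint.** SAP Table 2 lists NCA Cmax and tmax among the primary PK endpoints, if the data allow it. SAP Table 3 defines tmax as "Time [days] to reach peak or maximum observed concentration following drug administration" and Cmax likewise as an observed maximum. SAP 4.2.1 summarises tmax by n, median, minimum and maximum within cohort, route and weight category. The assigned sampling day is not a stratum.

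**Model-based results.** SAP Table 2 also lists model-derived concentrations, Cmax and AUC0-inf. It lists no model-derived tmax and does not say whether the NCA or the model-derived Cmax takes precedence.

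**The concern.** An observed tmax can only be a time at which a sample was taken. Each IM child has two samples near the likely peak, at most 14 days and about 30 days after dosing, and the earlier one is set by randomisation. Two children with identical absorption can therefore be given tmax values more than three weeks apart. Pooling over assigned days mixes these readings, and the resulting median depends on the sampling grid and on the day each child drew.

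Protocol 4.2 says the study supports extrapolation from adults and choice of the paediatric dose. SAP Table 5 shows that adult Phase I IM subjects were each sampled at 8 and 24 hours and at 3, 5, 7, 14 and 30 days. A paediatric IM median of 30 days set beside an adult value from that denser grid could be taken for slower absorption in children when it is produced by the design.

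**Working it through.** **1. Sample count.** IM: 1 (assigned early day) + 4 (Days 31, 92, 183, 366) = 5. IV: 5 + 1 (end of infusion) = 6. Both match Protocol 4.2.1: "the total number of samples per participant is up to 5 samples for IM administration and 6 samples for IV administration".

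**2. Inputs for the illustration.** Protocol 4.2.1 says 366 days cover about 4 half-lives, so the half-life is 366/4 = 91.5 days and ke = ln 2/91.5 = 0.00758 per day. The documents give no absorption rate, so a range is assumed. Later samples are placed at 30 days post-dose and beyond, as in the protocol.

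**3. Formulas.** C(t) ∝ exp(−ke·t) − exp(−ka·t), and true tmax = ln(ka/ke)/(ka − ke).

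**4. Worked case, absorption half-life 3 days.** ka = ln 2/3 = 0.2310, and true tmax = ln(30.5)/0.2235 = 15.3 days. In relative units C is 0.478 at 3 days, 0.750 at 7, 0.828 at 10, 0.860 at 14 and 0.796 at 30; the true peak is 0.861. Children assigned Day 4 or Day 8 have their larger value at 30 days and read tmax = 30. The others read 10 and 14. Cmax relative to the true peak is 0.92, 0.92, 0.96 and 1.00.

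**5. Noise-free tmax readings at nominal times, half-life 91.5 days.**

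| Absorption half-life, days (assumed) | True tmax | Day 4 child | Day 8 | Day 11 | Day 15 | Median, equal mix | Same curve on the adult Phase I IM grid |
|---|---|---|---|---|---|---|---|
| 1.1 | 7 | 3 | 7 | 10 | 14 | 8.5 | 7 |
| 2 | 11.3 | 30 | 7 | 10 | 14 | 12 | 14 |
| 3 | 15.3 | 30 | 30 | 10 | 14 | 22 | 14 |
| 4 | 18.9 | 30 | 30 | 30 | 14 | 30 | 14 |
| 5 | 22.2 | 30 | 30 | 30 | 30 | 30 | 30 |

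Beyond a true tmax of about 20 days, C(30) exceeds C(14) and every child reads 30.

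**6. Simulation with variability.** There were 200,000 children per scenario, with typical true tmax of 7, 14, 21 or 28 days. Assumed values were CV of ka 30% or 60%, CV of ke 30%, residual error 10% or 20%, and the Visit 2 and Visit 3 windows.

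- 88% to 99.9% of observed tmax values fell on the assigned visit or Visit 3.
- The share on the assigned visit was 63–77% for a typical true tmax of 7 days, 44–50% for 14, 23–28% for 21 and 8–16% for 28.
- Median observed tmax was 11–13 days for a true median of 7, 30 for 14, and 31–32 for 21.
- The correlation of observed with true tmax was 0.12 to 0.60.

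**7. Cmax.** Over true tmax of 5 to 28 days, the noise-free ratio of observed to true peak was 0.88 to 1.00 at a 91.5-day half-life, and 0.82 to 1.00 over half-lives of 60 to 100 days. In the simulation the geometric mean ratio by assigned day ran from 0.90 to 1.05. Within a scenario the assigned days differed by about 2 to 14 percentage points.

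**The case against.** Much of the design is deliberate and sound. Protocol 4.2.1 keeps sampling sparse because of the participants' age, spreads the early days on purpose, and puts population methods first, with NCA only if the data allow. SAP 4.2.1.1 and 4.2.1.2 list actual sampling times and plot individual profiles against them. No hypothesis is tested. All of this stands, but none of it changes the tmax summary: an observed maximum always exists, and neither document states when the data are too sparse to report it. SAP 4.2.1 refers to a sponsor guideline on PK evaluation and 4.2.1.3 speaks of reportable parameters. That guideline may contain such a rule, but it is not among the documents.

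Four stronger readings are tempting and are not supported.

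- **That Cmax also describes the assigned day.** With a half-life near 90 days the curve is flat around its peak, so the error is small. With absorption half-lives of 2 to 4 days, the assigned day contributes an SD of about 0.048 to 0.011 to log Cmax. Between two six-child cells that is √(2/6) × 0.048 = 2.8% at most, against about 12 to 17% from an assumed between-child CV of 20 to 30%.
- **That tmax can only be one of two values, always governed by the assigned day.** Windows, unscheduled samples (SAP 3.3.7.2) and assay noise make it nearly always, not always. With slow absorption most children read Day 31 whatever day they drew.
- **That the early-day list should be re-blocked by route and age group.** SAP section 2 says enrolment has stopped with 46 participants, so this would reach no one. Protocol 6.3 gives the ratio and is silent on blocking, so simple randomisation would be an inference.
- **That early-day concentration rows will be suppressed.** SAP 4.2.1.1 says "the serum concentrations for each scheduled time point will be summarized based on the PKS". SAP 3.3.1 still shows median, minimum and maximum at n = 3 and minimum and maximum below that, and SAP 4.2.1 includes an all-weights stratum.

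**Conclusion.** The point holds for IM tmax. Following the SAP as written would print, as a primary PK result, a median tmax pooled over assigned days that is not interpretable as a peak time. That nearly every value falls on the assigned visit or Visit 3 follows from the schedule and the definition. How the readings divide between the two depends on the absorption rate, which the documents do not give. The numerical illustrations rest on a one-compartment curve, a half-life of about 91.5 days taken from the protocol, and assumed absorption and variability.

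For Cmax the effect is a modest downward bias that varies with the assigned day: 0 to 12% in the noise-free curves, up to 18% if the half-life were 60 days. NCA Cmax remains a usable exposure measure.

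The consequence is limited to how a descriptive endpoint is reported and compared with adult data. It affects no test and calls for no change to sampling.

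**What to change.** In SAP 4.2.1 and 4.2.1.3, for the IM route:

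1. Do not summarise NCA tmax pooled over assigned sampling days. Either tabulate it by assigned day, or give it only in listings with the assigned day beside each value.
2. Report tmax from the population PK model and add it to the model-derived results in SAP Table 2.
3. Name the model-derived Cmax already in SAP Table 2 as the main IM peak result. Keep the NCA Cmax summary with a footnote that it is the highest of the scheduled samples and may understate the peak by an amount that depends on the assigned day.

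This costs a few lines of SAP text and a change to the table shells, with no new samples and no protocol amendment. The downside is that the IM peak time then rests on the model's absorption estimate. The model also uses the adult studies, and SAP 4.2.1.9 already requires shrinkage in Ka to be evaluated; that figure should be reported beside the model-derived tmax.
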